## 11.0 DATA SUBMISSION SCHEDULE

Case Report Form	Submission Schedule
Original Consent Registration Eligibility Checklist Medical History Treatment History Radiation History Transplant History Vital Signs Labs – Hematology Labs – Chemistry Disease Assessment Skeletal Survey/Plasmacytoma Evaluation Bone Marrow Biopsy	Original Consent: Before initiation of any non-standard of care procedures  Registration and Eligibility Checklist: At time of enrollment  All others: Within 28 days of enrollment
Vital Signs Labs – Hematology Labs – Chemistry Disease Assessment Response Assessment Skeletal Survey/Plasmacytoma Evaluation Bone Marrow Biopsy Study Drug Dosing Record	Within 28 days of end of each cycle  Note: Some forms must be completed multiple times per cycle
Correlative Studies	Within 28 days of sample collection
Adverse Events	To be completed throughout study participation; as per guidelines in section 13.1
Off Study Vital Signs Labs – Hematology Labs – Chemistry Disease Assessment Form Response Assessment Form Skeletal Survey/Plasmacytoma Evaluation Bone Marrow Biopsy Form	Within 28 days of end of study visit
Survival Form	Within 28 days of follow-up

## 12.0 CORRELATIVE STUDIES

Bone marrow and peripheral blood samples will be taken prior to treatment, at time of complete response, and/or at end of study.

The following samples will be collected at all time points:

- Bone marrow aspirate: 6-10 mL divided between two EDTA (lavender top) tubes.
- Peripheral blood for viable PBMC: 60 mL collected in 6 large EDTA (lavender top) tubes.
- Peripheral blood for plasma: 10 mL collected in 1 EDTA (lavender top) tube.

Bone marrow aspirate samples will be pooled, and mononuclear cells will be purified over Ficoll. Resulting BM mononuclear cells will be divided into 1) viable cells cryopreserved at  $10^7$ /vial, and 2) cell pellet for nucleic acid. Plasma and from bone marrow will be divided into 2mL aliquots and frozen at  $-80^{\circ}\text{C}$ .

Peripheral blood mononuclear cells (PBMC) will similarly be isolated by Ficoll preparation from the pooled peripheral blood lavender top tubes and will be viably cryopreserved.

Plasma will be divided into 2mL aliquots and frozen at  $-80^{\circ}\text{C}$ .

Fresh PBMC or BM mononuclear cells may also be used for correlative studies at the discretion of the principal investigator.

All samples are to be delivered to the Siteman Cancer Center Tissue Procurement Core ([name], Director) during their normal operating hours. Specimens will be identified by initials and study number at the Tissue Procurement Core, and samples will be processed appropriately.

Contact information for questions regarding sample procurement only:

[name]., Ph.D.  
Siteman Cancer Center Tissue Procurement Facility  
BJC Institute of Health  
[name]  
[contact]  
[contact]  
Email: [[contact]](mailto:[contact])

## 13.0 SAFETY MONITORING, DATA AUDITING, AND REQUIRED REPORTING OF EVENTS

### 13.1 Adverse Events

**Definition:** any unfavorable medical occurrence in a human subject including any abnormal sign, symptom, or disease.

**Grading:** the descriptions and grading scales found in the revised NCI Common Terminology Criteria for Adverse Events (CTCAE) version 4.0 will be utilized for all toxicity reporting. A copy of the CTCAE version 4.0 can be downloaded from the CTEP website.

**Attribution (relatedness), Expectedness, and Seriousness:** the definitions for the terms listed that should be used are those provided by the Department of Health and Human Services' Office for Human Research Protections (OHRP). A copy of this guidance can be found on OHRP's website: (<http://www.hhs.gov/ohrp/policy/AdvEvtGuid.htm>).

All AEs, regardless of relationship to study drug, will be followed from first day of study treatment until 30 days following the last day of study treatment or until the start of a new chemotherapy, whichever is sooner. All AEs resulting in death within 30 days following the last day of study treatment will be recorded without regards to new chemotherapy. Thereafter, any death while off study but reasonably related to study drug(s) will be recorded, regardless of the proximity to study treatment.

All AEs should be recorded in the Case Report Forms (CRFs). The CRFs should include the duration, outcome, intensity, attribution, dose delays/dose modifications, and seriousness.

The descriptions and grading scales found in the revised NCI Common Terminology Criteria for Adverse Events (CTCAE) version 4.0 will be utilized for all toxicity reporting (see Appendix D).

#### 13.1.1 Regulatory Reporting of Internal AEs

When a trend of unexpected and reasonably related non-serious AEs is identified by the PI, these events are required to be reported to Amgen, HRPO, QASMC, and the FDA in a written report (Medwatch 3500 form, see Appendix E). The events should be then added to the consent form.

All grade 3 and 4 AEs that are serious and/or unexpected and reasonably related must be reported to Amgen, HRPO, QASMC, and the FDA in a written report (Medwatch 3500 form, see Appendix E).

All grade 5 (death) AEs must be reported to Amgen, HRPO, QASMC, and the FDA in a written report (Medwatch 3500 form, see Appendix E).

### 13.1.2 Regulatory Reporting of External AEs

Any event or summary of adverse events that are provided to the investigator or study chair should be submitted to QASMC and/or HRPO for review.

## 13.2 Unanticipated Problems

### Definition:

- unexpected (in terms of nature, severity, or frequency) given (a) the research procedures that are described in the protocol-related documents, such as the IRB-approved research protocol and informed consent document; and (b) the characteristics of the subject population being studied;
- related or possibly related to participation in the research (in this guidance document, possibly related means there is a reasonable possibility that the incident, experience, or outcome may have been caused by the procedures involved in the research); and
- suggests that the research places subjects or others at a greater risk of harm (including physical, psychological, economic, or social harm) than was previously known or recognized.

## 13.3 Noncompliance

**Definition:** failure to follow any applicable regulation or institutional policies that govern human subjects research or failure to follow the determinations of the IRB. Noncompliance may occur due to lack of knowledge or due to deliberate choice to ignore regulations, institutional policies, or determinations of the IRB.

## 13.4 Serious Noncompliance

**Definition:** noncompliance that materially increases risks, that results in substantial harm to participants or others, or that materially compromises the rights or welfare of participants.

## 13.5 Protocol Exceptions

**Definition:** A planned deviation from the approved protocol that are *under the research team's control*. Exceptions apply only to a single participant or a singular situation.

Pre-approval of all protocol exceptions must be obtained prior to the event, unless

taken to avoid or eliminate immediate harm to a participant/participants. If taken to avoid or eliminate immediate harm to a participant report within 24 hours.

### **13.6 Pregnancy**

Pregnancy of a female participant or the female partner of a male participant while enrolled on this clinical trial or up to three months following administration of study drug(s) is a reportable event (Medwatch 3500 form, See Appendix E). If the participant is on study drug(s) at the time of pregnancy it must be discontinued immediately.

The pregnant female will be followed until completion of the pregnancy. The Investigator will be required to report the results of the pregnancy (follow-up to the original Medwatch 3500 form).

If the outcome of the pregnancy meets a criterion for immediate classification as a grade 5 event—spontaneous abortion (any congenital anomaly detected in an aborted fetus is to be documented), stillbirth, neonatal death, or congenital anomaly—the Investigator should report the event per the guidelines below.

### **13.7 Reporting to the Human Research Protection Office (HRPO) and the Quality Assurance and Safety Monitoring Committee (QASMC) at Washington University**

The PI is required to promptly notify the IRB of the following events:

- Any unanticipated problems involving risks to participants or others which occur at WU, any BJH or SLCH institution, or that impacts participants or the conduct of the study.
- Noncompliance with federal regulations or the requirements or determinations of the IRB.
- Receipt of new information that may impact the willingness of participants to participate or continue participation in the research study.

These events must be reported to the IRB within **10 working days** of the occurrence of the event or notification to the PI of the event. The death of a research participant that qualifies as a reportable event should be reported within **1 working day** of the occurrence of the event or notification to the PI of the event.

### **13.8 Reporting to the FDA**

The conduct of the study will comply with all FDA safety reporting requirements. **PLEASE NOTE THAT REPORTING REQUIREMENTS FOR THE FDA DIFFER FROM REPORTING REQUIREMENTS FOR HRPO/QASMC.** It

is the responsibility of the investigator to report any unanticipated problem to the FDA as follows:

- Report any unexpected fatal or life-threatening adverse experiences associated with use of the drug (i.e., there is a reasonable possibility that the experience may have been caused by the drug) by telephone or fax no later than **7 calendar days** after initial receipt of the information. A life-threatening adverse experience is defined as any adverse drug experience that places the subject (in the view of the investigator) at immediate risk of death from the reaction as it occurred, i.e., it does not include a reaction that, had it occurred in a more severe form, might have caused death.
- Report any serious, unexpected adverse experiences, as well as results from animal studies that suggest significant clinical risk within **15 calendar days** after initial receipt of this information. A serious adverse drug experience is defined as any adverse drug experience occurring at any dose that results in any of the following outcomes:
  - Death
  - A life-threatening adverse drug experience
  - Inpatient hospitalization or prolongation of existing hospitalization
  - A persistent or significant disability/incapacity (i.e., a substantial disruption of a person's ability to conduct normal life functions)
  - A congenital anomaly/birth defect
  - Any other experience which, based upon appropriate medical judgment, may jeopardize the subject and may require medical or surgical intervention to prevent one of the outcomes listed above

An unexpected adverse drug experience is defined as any adverse drug experience, the specificity or severity of which is not consistent with the current investigator brochure (or risk information, if an IB is not required or available).

All MedWatch forms will be sent by the investigator or investigator's team to the FDA at the following address or by fax:

Food and Drug Administration  
Center for Drug Evaluation and Research  
Division of Oncology Drug Products  
[name]  
[name]  
FAX: [name]

### **13.9 Reporting to Amgen**

All required forms will be sent to Amgen Global Safety by [contact], or at the following email address (with secure email connection with Amgen only): [[contact]](mailto:[contact]).

### 13.10 Timeframe for Reporting Required Events

Deaths	
Any reportable death while on study or within 30 days of study	Immediately, within 24 hours, to PI, FDA, Amgen, and the IRB
Any reportable death while off study	Immediately, within 24 hours, to PI, FDA, Amgen, and the IRB
Adverse Events/Unanticipated Problems	
Any reportable adverse events as described in Sections 12.1 and 12.2 (other than death)	Immediately, within 24 hours to PI, FDA, and within 10 working days to the IRB
All adverse events regardless of grade and attribution should be submitted cumulatively	Include in DSM report
Non-Compliance and Serious Non-Compliance	
All noncompliance and serious noncompliance as described in Sections 12.3 and 12.4	Immediately, within 24 hours, to PI and within 10 working days to the IRB
Pregnancy	
Pregnancy	Immediately, within 24 hours, to PI, FDA, Amgen, and the IRB

### 14.0 DATA AND SAFETY MONITORING PLAN

In compliance with the Washington University Institutional Data and Safety Monitoring Plan, the Principal Investigator will provide a Data and Safety Monitoring (DSM) report to the Washington University Quality Assurance and Safety Monitoring Committee (QASMC) semi-annually beginning six months after accrual has opened (if at least five patients have been enrolled) or one year after accrual has opened (if fewer than five patients have been enrolled at the six-month mark).

During the phase I dose escalation, the Principal Investigator will review all patient data at least monthly (or before each dose-escalation if occurring sooner than monthly), and provide a semi-annual report to the Quality Assurance and Safety Monitoring Committee (QASMC). During the phase II, the Principal Investigator will review all patient data at least every six months, and provide a semi-annual report to the QASMC. This report will include:

- HRPO protocol number, protocol title, Principal Investigator name, data coordinator name, regulatory coordinator name, and statistician
- Date of initial HRPO approval, date of most recent consent HRPO approval/revision, date of HRPO expiration, date of most recent QA audit, study status, and phase of study

- History of study including summary of substantive amendments; summary of accrual suspensions including start/stop dates and reason; and summary of protocol exceptions, error, or breach of confidentiality including start/stop dates and reason
- Study-wide target accrual and study-wide actual accrual
- Protocol activation date
- Average rate of accrual observed in year 1, year 2, and subsequent years
- Expected accrual end date and accrual by cohort
- Objectives of protocol with supporting data and list the number of participants who have met each objective
- Measures of efficacy
- Early stopping rules with supporting data and list the number of participants who have met the early stopping rules
- Summary of toxicities separated by cohorts with the number of dose-limiting toxicities indicated
- Abstract submissions/publications
- Summary of any recent literature that may affect the safety or ethics of the study

The study principal investigator and Research Patient Coordinator will monitor for serious toxicities on an ongoing basis. Once the principal investigator or Research Patient Coordinator becomes aware of an adverse event, the AE will be reported to the HRPO and QASMC according to institutional guidelines.

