## 2.0 OBJECTIVES

### 2.1 Primary Objectives

- **Phase 1: Part 1-** To determine the Maximal Tolerated Dose (MTD) of carfilzomib in combination with pegylated liposomal doxorubicin (PLD), in participants with relapsed or refractory multiple myeloma. **Part 2-** To determine the Maximal Tolerated Dose (MTD) of carfilzomib in combination with PLD and dexamethasone, in participants with relapsed or refractory multiple myeloma.
- **Phase 2:** To evaluate the efficacy and toxicity of carfilzomib in combination with PLD and dexamethasone in participants with relapsed or refractory multiple myeloma.

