### **15.0 ENDPOINTS**

#### **15.1 Primary Outcome Analyses**

The primary endpoint for each arm of the phase II portion of this trial is the proportion of confirmed tumor responses. A confirmed response is defined to be a CR, VGPR, or PR noted as the objective status. Response will be evaluated using up to 12 cycles of treatment. All participants meeting the eligibility criteria who have signed a consent form and have begun treatment will be evaluable for response.

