## **16.0 STATISTICAL ANALYSIS**

In the Phase 2 portion, the largest success proportion where the proposed treatment regimen would be considered ineffective in this population is 20%, and the smallest success proportion that would warrant further treatment is 40%. The following one-stage design uses 24 participants to test the null hypothesis that the true success proportion is at most 20%.

Enter 24 participants into the phase 2 portion of the study. If 7 or fewer successes are observed, we will consider this treatment ineffective in this participant population. If 8 or more successes are observed, we may recommend further testing of the regimen in subsequent studies in this population.

Power and Significance Level: Assuming that the number of successes is binomially distributed, the significance level is 0.10, i.e. there is a 10% chance of finding the drug to be effective when it truly is not. The probability of declaring that this regimen warrants further study (i.e. statistical power) under various success proportions, and the probability of stopping after the first stage can be tabulated as a function of the true success proportion.

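### Toxicity is a phase II primary objective, but the plan gives it no endpoint, no analysis and no prespecified criterion for pausing phase II accrual

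*Combined protocol and SAP*

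**What the plan says.** Section 2.1 states the phase II primary objective as "To evaluate the efficacy and toxicity of carfilzomib in combination with PLD and dexamethasone in participants with relapsed or refractory multiple myeloma". Section 15.1 then names one primary endpoint: "The primary endpoint for each arm of the phase II portion of this trial is the proportion of confirmed tumor responses". Section 15.2 covers survival, progression-free survival and duration of response. Section 16 sets a one-stage test of the response proportion. Its last sentence mentions the chance of stopping at a first stage, but no first stage is defined. Section 5.3 gives a response cut-off only.

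Section 14.0 lists among the contents of the monitoring report: "Early stopping rules with supporting data and list the number of participants who have met the early stopping rules". On the frequency of review it says: "During the phase II, the Principal Investigator will review all patient data at least every six months". In phase I the corresponding review is at least monthly, or before each escalation if sooner.

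The only toxicity rule at trial level is the 3+3 escalation rule in Sections 5.2.1 and 5.2.2, based on Cycle 1 DLTs (Section 6.1). Section 5.3 counts phase I participants treated at the MTD towards phase II.

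**The concern.** Half of a primary objective has no estimand, estimate or decision attached to it. The monitoring report also asks for results against stopping rules, and none is defined for phase II.

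This matters because the phase II dose rests on little data. A 3+3 level is cleared on 3 to 6 participants and on Cycle 1 events alone, so a dose with a high DLT rate can reach phase II. If it does, nothing fixed in advance says when accrual should pause, and the scheduled full-data review is less frequent than in phase I.

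**Working it through.** The plan states no toxicity threshold or operating characteristic, so there is no figure to reproduce. The absence is established by reading Sections 2.1, 5.2, 5.3, 6, 8.1, 14, 15 and 16 together. The arithmetic below sizes the consequence and tests a possible remedy.

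**Review interval.** Section 5.5 plans 1 to 2 participants per month. Over six months that is 6 × 1 = 6 to 6 × 2 = 12 participants, which is 35% to 71% of 17 or 25% to 50% of 24. Accrual of 17 takes 17/2 = 8.5 to 17/1 = 17 months, so one or two six-monthly reviews fall before it ends. With 6 carried over from phase I, the 11 new participants take 5.5 to 11 months, so at most one review does.

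**Chance that a level passes the 3+3.** A level passes with 0 DLTs in 3, or 1 in 3 followed by 0 in 3: (1−p)³ + 3p(1−p)²·(1−p)³.
- p = 0.40: 0.216 + 0.093 = 0.31.
- p = 0.50: 0.125 + 0.047 = 0.17.

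**Illustrative boundary.** The assumptions are a reference rate of 1/3 (the lowest rate at which the 3+3 stops, 2 of 6), a Beta(0.67, 1.33) prior, and a check after each participant from the third. Accrual pauses when the posterior probability that the rate exceeds 1/3 is at least 0.90. For example, 3 of 3 gives 0.97 (pause) and 2 of 3 gives 0.82 (continue). The full boundary is 3 of 3–4, 4 of 5–6, 5 of 7–8, 6 of 9–11, 7 of 12–13, 8 of 14–15 and 9 of 16–17.

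**Operating characteristics.** These come from exact forward recursion over the cumulative DLT count. At each participant the probability at count x splits into x (weight 1−p) and x+1 (weight p), and mass at or above the boundary is removed as paused. Three ways of counting were compared for a total of 17:
- A: from zero, ignoring phase I.
- B: cumulative, starting from 0/3 or 1/6, weighted by the two terms of the pass formula.
- C: afresh on newly enrolled participants (assumed 11 new, 6 carried over).

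| True rate | A: P(pause) | B: P(pause) | C: P(pause) |
|---|---|---|---|
| 20% | 0.04 | 0.002 | 0.04 |
| 25% | 0.09 | 0.006 | 0.08 |
| 50% | 0.68 | 0.25 | 0.59 |
| 60% | 0.89 | 0.51 | 0.81 |

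As a check of B at 50%, the weights are 0.125/0.172 = 0.73 for a 0/3 start and 0.27 for a 1/6 start. The pause probabilities from those starts are 0.283 and 0.146, and 0.73 × 0.283 + 0.27 × 0.146 = 0.25.

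Mean exposure under A is 10.3 at 50% and 7.5 at 60%; under B it is 15.9 and 14.6. A does not describe this trial if phase I participants are counted, because they have already passed. From 0/3 the boundary cannot be reached before participant 8, and from 1/6 not before participant 11.

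**The case against.** The plan is not without oversight. Section 14.0 has the investigator and coordinator monitor serious toxicity continuously, and six months is the longest permitted gap between full reviews. Section 13.10 sets 24-hour reporting, the QASMC receives semi-annual reports that cover accrual suspensions, and Section 8.1 allows the centre to close the study. The monitoring-report item could also be read as covering the phase I rule or the participant-level removal criteria, since it counts participants.

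A reader might therefore infer too much in two ways: that the protocol has no stopping rule at all, or that phase II would fill whatever the toxicity. The documents support neither. Phase I has a rule that stops escalation, and accrual can be suspended at discretion. What is missing is a criterion fixed in advance for phase II.

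Two further objections carry weight. At the Part 2 starting level the carfilzomib and PLD doses have already passed Part 1. If the DLT rate were similar with and without dexamethasone, passing both would have probability about 0.31² = 0.10 at 40% and 0.17² = 0.03 at 50%, so a very toxic phase II dose is less likely than one 3+3 suggests. And a boundary applied cumulatively after phase I protects weakly, as column B shows. The first lowers the urgency. The second argues for designing the boundary properly, not for leaving it out. Neither supplies the missing analysis of a primary objective.

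The particular Bayesian boundary is one choice among several.

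**Conclusion.** The point holds. Toxicity is a phase II primary objective without an endpoint, an analysis or a prespecified trigger for pausing accrual, and the stopping-rule item in Section 14.0 has nothing in phase II to refer to. Any pause rests on discretion, with 6 to 12 participants enrolling between required full-data reviews.

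The benefit of a boundary depends on how phase I participants are counted. At a true 50% the illustrative rule pauses with probability 0.25 if applied cumulatively and 0.59 if started afresh, so starting afresh is the more useful form.

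These figures assume a total of 17, a reference rate of 1/3 that the documents do not state, a 0/3 or 1/6 start for B, 6 carried over for C, and Cycle 1 outcomes known at once. With 28-day cycles and 1 to 2 entries per month, one or two more participants could enrol before an outcome is known. This is a correction that should be made, not evidence that participants are unmonitored.

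**What to change.** 1. Reconcile the phase II sample size, 17 in Section 5.3 against 24 in Section 16. Any boundary depends on it.
2. State how many phase I participants carry over and whether they count towards the toxicity boundary.
3. Add to Section 16 a toxicity boundary that pauses phase II accrual for QASMC review, preferably counted afresh on new participants. The sponsor sets the acceptable rate. Give operating characteristics that reflect the 3+3 already passed.
4. Refer to that boundary in the stopping-rule item of Section 14.0, and remove or define the first stage mentioned in Section 16.
5. Add toxicity to Section 15.1, with its analysis set and an exact confidence interval at a stated level, as a primary result beside response. A boundary on Cycle 1 events cannot see later toxicity, so summarise later cycles separately.

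The cost is wording and a short calculation; DLT counts already go into the report to the QASMC. In the illustration the downside is about a 4% to 8% chance of an unnecessary pause when the true rate is 20% to 25%, and a pause for review is not a closure.
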